10.3 Change from Baseline

Change from baseline (CFB) will be calculated as:

$$(\text{post-baseline} - \text{baseline}).$$

CFB will be calculated for patients with both a baseline and post-baseline value as applicable.

10.4 Percentage Change from Baseline

Percent CFB will be calculated, where applicable, as:

$$(\text{CFB}/\text{baseline}) * 100.$$

If a baseline value has not been recorded for a parameter, then percent CFB will be missing for that parameter.

If baseline and post baseline are rates the following formula will be used:

$$\left(\frac{\text{Post baseline score}/\text{count} * \text{baseline duration}}{\text{Baseline score}/\text{count} * \text{post baseline duration}} - 1 \right) * 100$$

10.5 Time Conversion

Time conversion will follow the rules described below:

- 1 week = 7 days,
- 1 Month = 30.4375 days,
- 1 year = 365.25 days.

10.6 Patient Disposition

The time to treatment discontinuation expressed in day is defined as:

the date of last administration – the date of 1st IMP spray intake +1 day.

The time to study discontinuation expressed in day is defined as:

End of study day – date of randomization + 1 day.

Where the date of the 1st IMP spray intake (e.g., IMP start date) will be retrieved from the eCRF “PK sample collection form” and, if missing, from the eDiary first spray date for Period 1 whereas, the end of treatment date will be the latest date between the end of treatment date coming from eCRF “End of treatment Period 1” form and “End of treatment Period 2” form.

Censoring rules for time to event analysis, censoring rules are defined in [Section 12.1](#).

10.7 Duration of Treatment

The duration of study drug exposure expressed in days will be defined for each study drug as:

- the date of last administration – the first day of administration +1 day.

The mean duration of study drug exposure expressed in patient-time will be defined as follows:

- The mean duration (patient-year) = $(\sum_{i=1}^{i=n} D_i) / 365.25$
- The mean duration (patient-week) = $(\sum_{i=1}^{i=n} D_i) / 7$

With n being the number of patients within the Safety Analysis Set and i=1,2, 3,...,n, and, with Di being the duration of treatment (in days) for patient i.

The IMP start date will be retrieved from the eCRF “PK sample collection form” for each treatment period whereas the end of treatment date for each period will respectively be coming from eCRF “End of treatment Period 1” form and “End of treatment Period 2” form. However, if the information is missing on the eCRF “PK sample collection”, the first IMP spray date will be retrieved from the eDiary first spray date of each treatment period.

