10.12 Disease History

As part of Disease history description, the following parameters will be derived:

Time since diagnosis of MS (years)

$$(\text{Date of Informed consent} - \text{Date of MS diagnosis} + 1) / 365.25;$$

Age at diagnosis of MS (years)

$$(\text{year of MS diagnosis} - \text{year of Birth} + 1)$$

Time since onset of spasticity due to MS (years)

$$(\text{Date of Informed consent} - \text{Date of onset of spasticity due to MS} + 1) / 365.25;$$

Age at onset of spasticity due to MS (years)

$$(\text{year of onset of spasticity due to MS} - \text{year of Birth} + 1);$$

Time between MS diagnosis and onset of spasticity due to MS (years)

$$(\text{Date of onset of spasticity due to MS} - \text{Date of MS diagnosis} + 1) / 365.25;$$

Time between MS diagnosis and onset of spasticity due to MS (months)

$$(\text{Date of onset of spasticity due to MS} - \text{Date of MS diagnosis} + 1) / 30.4375.$$

The following conversion will be applied as appropriate:

- Time since last relapse (months) = Time since last relapse (years) * 12,
- Time since last relapse (months) = Time since last relapse (days) / 30.4375.

Age at diagnosis of MS and age at onset of spasticity due to MS are only using year because only year of birth is planned to be collected.

If date of MS diagnosis and/or date of onset of spasticity due to MS are unknown or partial, they will be imputed as follow:

- if only day is missing, it will be imputed to the 15th of the month,
- If day and month are missing, they will be imputed to the 30 June of the year,
- However, if any of these dates fall after the informed consent date, they will be set to the informed consent date. If the date of onset of spasticity due to MS before the date of MS diagnosis due to imputation rule, it will be set to the date of MS diagnosis.

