12.3.1.1 Duration of Therapy

The extent of exposure will be for each study drug (e.g., Nabiximols or placebo) the total number of days of administration of IMP, ignoring temporary drug discontinuation, within the designated treatment period.

The duration of exposure (as defined in [Section 10.7](#)) will be summarized descriptively as quantitative variable (number, mean, SD, median, Q1, Q3, minimum and maximum) but also presenting the total number of days and the mean number of days (expressed in patient-week) as defined in [Section 10.7](#).

The number and percentage of patients with an extent of exposure within a predefined study day range will also be presented for each of the following categories and the cumulative distribution according to these categories:

- Day 1 to 7,
- Day 8 to 14,
- Day 15 to 21,
- Day 21.

Extend to exposure will also be summarized per treatment arm by subgroups of interest as presented in [Table 12.1-1](#).

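### SAP 10.7 labels total patient-time as mean exposure, and SAP 10.12 adds a whole year to age at MS diagnosis and at spasticity onset

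*SAP*

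**What the plan says.** **Exposure.** SAP 10.7 defines each patient's duration on a drug as "the date of last administration – the first day of administration +1 day". It continues: "The mean duration of study drug exposure expressed in patient-time will be defined as follows". Two formulas follow. The patient-year version is the sum of the D_i over i = 1 to n, divided by 365.25. The patient-week version is the same sum divided by 7. The symbols are explained as "With n being the number of patients within the Safety Analysis Set and i=1,2, 3,...,n, and, with Di being the duration of treatment (in days)", so n enters only as the upper limit of the sum.

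SAP 12.3.1.1 asks for the number, mean, SD, median, quartiles and range of the per-patient durations, "also presenting the total number of days and the mean number of days (expressed in patient-week", and refers back to 10.7. It does not ask for the patient-year version.

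**Ages.** SAP 10.12 defines age at MS diagnosis as year of diagnosis minus year of birth plus 1, and age at spasticity onset in the same way. Its explanation is "Age at diagnosis of MS and age at onset of spasticity due to MS are only using year because only year of birth" is to be collected. SAP 12.2.5 lists both ages among the disease characteristics.

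**The concern.** A sum over patients divided by 7 changes the unit from days to weeks but does not average over patients. The label and the formula in 10.7 therefore describe different quantities, and 12.3.1.1 carries the label *mean* into the exposure summary. The SAP does divide where it wants a mean over patients: in 10.8.2 the mean number of sprays is the total divided by the number of patients.

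For the ages, the likely source of the error is the neighbouring formulas. In 10.10 and in the other 10.12 durations, the +1 is one day, added to a difference of dates before dividing by 365.25 or 30.4375. In the two age formulas nothing is divided, so the same +1 is a full year. That only years are available explains why years are used. It does not explain adding one.

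At stake is the accuracy of one exposure row and two disease-history rows in the study report.

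**Working it through.** The documents give no numerical result for these quantities, so there is no stated figure to reproduce. The formulas are applied as written and then in corrected form.

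**1. Exposure**

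Inputs: 21 days of treatment per period (protocol 4.1); 190 planned patients and at least 170 completers (protocol 4.3 and SAP 8.2). Assumption for illustration: every patient counted takes the drug for the full 21 days.

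| Patients | Sum of D_i (days) | Sum / 7 | Sum / 365.25 | Weeks per patient | Years per patient |
|---|---|---|---|---|---|
| 190 | 190 × 21 = 3990 | 570 | 10.92 | 570 / 190 = 3.0 | 10.92 / 190 = 0.0575 |
| 170 | 170 × 21 = 3570 | 510 | 9.77 | 510 / 170 = 3.0 | 9.77 / 170 = 0.0575 |

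Under this assumption the row labelled as a mean is too large by a factor equal to the number of patients.

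**2. Which denominator**

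Exposure is defined for each drug, but n in 10.7 is the whole Safety Analysis Set. A patient who stops before Period 2 has no duration on the second drug. Assume 190 treated (95 per sequence), 10 per sequence stopping after Period 1, and everyone else taking 21 days of each drug:

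- Exposed to a given drug: 95 in Period 1 + 85 in Period 2 = 180.
- Sum: 180 × 21 = 3780 days = 540 patient-weeks.
- Divided by n = 190: 2.84 weeks. Divided by the 180 exposed: 3.0 weeks.

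Dividing by n as 10.7 defines it would therefore still be slightly wrong.

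**3. Age, average error**

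Let b and e be the positions of the birth date and the event date within their calendar years, each assumed uniform on 0 to 1.

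- Exact age = year difference + (e − b), and e − b averages 0. The year difference alone has average error 0 against exact age; with the +1 it is +1.0 year.
- Completed age = year difference, less 1 when the birthday has not yet been reached (probability 0.5). The year difference alone is 0 or 1 too high, average +0.5. With the +1 it is 1 or 2 too high, average +1.5.

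A simulation of 200,000 pairs of dates agrees: 1.00 and 1.50 with the +1, 0.00 and 0.50 without it.

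**4. Age, consistency within the SAP**

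Take birth year 1980, diagnosis on 15 June 2010 and consent on 15 June 2022.

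- Age at consent by 10.10, with birth set to 15 June when only the year is known: 42.0.
- Time since diagnosis by 10.12: 12.0.
- Implied age at diagnosis: 42.0 − 12.0 = 30.0.
- Age at diagnosis by 10.12: 2010 − 1980 + 1 = 31.

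The SAP's quantities do not add up: 31 + 12 = 43, not 42. If spasticity onset falls in the year of consent, the formula gives an onset age above the age at consent: by roughly 0.5 to 1.5 years under the 15 June rule, or by 1 or 2 years if completed age is recorded.

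**The case against.** The strongest reply on exposure is that the number is right and only the word is wrong. A sum of days divided by 7 or 365.25 is the usual expression for cumulative patient-time, and 10.7 itself speaks of patient-time, patient-years and patient-weeks. Placing it beside the total number of days does not prove that a mean was meant, since the pair could be one total in two units. This stands: the documents do not settle whether the label or the formula is the slip. The two still contradict each other, and either resolution needs an edit.

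A reader might infer that the trial will report no correct mean exposure. The documents do not support that. 12.3.1.1 also requires the ordinary mean, SD, median and range of the per-patient durations, which 10.7 defines correctly, and the total days and exposure categories are unaffected. A row of 570 weeks beside a mean of about 21 days would probably be noticed.

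A reader might also expect the age discrepancy to show within a single table. Age is listed under demographics (12.2.1), and the diagnosis and onset items under disease characteristics (12.2.5). The SAP does not say that they share a table.

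Finally, the age errors in step 3 rest on dates spread evenly over the year, and deleting the +1 leaves an average of +0.5 year against completed age. Both are true. With only years available, the plain difference is nevertheless unbiased for exact age.

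**Conclusion.** Both slips are in the current SAP text, and no other section corrects them. In 10.7 and 12.3.1.1, a total is called a mean; under the illustration above it reads 570 weeks against 3.0 per patient. In 10.12, two ages are overstated by 1.0 year on average against exact age, given evenly spread dates, and disagree with the SAP's own age at consent and time since diagnosis.

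It would go too far to say that the exposure and disease-history tables as a whole are wrong. One patient-week row and two age rows are affected. The *time since* and *time between* items add a single day (1/365.25 = 0.003 year), which is negligible.

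Whether the rows will be produced at all is open. The SAP addendum, written after the decision to stop the study early, abbreviates the reporting, and its strategy table names neither exposure nor disease history. The errors appear only if those summaries are run as specified. All the items are descriptive, so the efficacy analyses, type I error and power are unaffected. This is a minor correction.

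**What to change.** - **10.7 and 12.3.1.1:** rename the quantity as total exposure in patient-weeks and patient-years and keep the formulas. This is the simpler choice, because the mean of days is already reported. If a mean in weeks or years is wanted, divide by the number of patients exposed to that drug, not by the whole Safety Analysis Set.
- **10.12:** delete the +1 from age at MS diagnosis and age at spasticity onset. Leave the one-day +1 in the date-based durations.

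The cost is a change of wording or denominator for the two exposure formulas and their mention in 12.3.1.1, plus two small formula edits, with matching changes to the table programs if these summaries are produced. No other analysis changes.

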10.8 IMP Dosing

10.8.1 Study Phases Start and Stop Dates used to summarize IMP Dosing

The titration phase

- Start of the titration phase during Period 1 is defined as:

Min(randomization date, 1st IMP dosing date)

- Start of the titration phase during Period 2 is defined as:

Min(the date of IRT call for Period 2, Visit 6 date)

- End of the titration phase during Period 1 is defined as:

Min(the day preceding Visit 4 date, the last dose date during Period)

- End of the titration phase during Period 2 is defined as:

Min(the day preceding Visit 8 date, the last dose date during Period 2)

The maintenance phase

- Start of the of the maintenance phase during Period 1 is defined as:
the date of Visit 4,
- Start of the of the maintenance phase during Period 2 is defined as:
the date of Visit 8,
- End date of the maintenance phase during Period 1 is defined as:
Min(Visit 5 date, the date of the last dose of study drug)
- End date of the maintenance phase during Period 2 is defined as:
the date of the last dose of study drug

10.8.2 Number of Sprays Summary

For each parameter presented in this section,

- **The start and stop date** of each studied period is defined in [Section 10.8.1](#). These studied periods are defined for Period 1 and Period 2 to allow summaries by treatment arm.
- **The duration of each studied period** will then be derived using the appropriate treatment phase (titration, maintenance) for each treatment period as: Date of stop – date of start + 1 day
- eDiary information will be used to retrieve the total daily number of sprays taken by a given patient
- **A non-missing diary day** is defined as any day where the eDiary is filled but IMP dosing information are fully included or partial (missing morning or evening dose) or totally missing.
- **A missing diary day** is defined as any day where the eDiary is not filled
- **Imputation rule:** for a non-missing diary day where IMP dosing information is partial or missing the number of sprays taken on that missing morning or evening administration will be imputed to “0” to derive the total daily number of spray taken.

The mean number of sprays is defined for each treatment arm as the total number of sprays taken during the studied period divided by the number of patients within the studied period regardless intermittent IMP discontinuation.

The patient mean number of daily sprays a patient has taken on a daily basis is calculated for each studied period as the total number of sprays taken divided by the number of non-missing diary days for each patient.

Based on the above the patient mean number of daily sprays (also called mean use of IMP) will also be categorized as follows:

- ≤ 6 sprays,
- 6 sprays and ≤ 12 sprays,
- 12 sprays.

The total number of daily sprays is referring to the total number of sprays a patient has taken on a daily basis for a studied period.

The patient median number of daily sprays refers to the median number of sprays a patient has taken on a daily basis for a studied period.

The patient mode number of daily sprays refers to more frequently occurring number of sprays a patient has taken on a daily basis for a studied period. If a patient has more than one mode or no mode determined then the patient has a ‘missing’ mode.

The patient maximal number of daily sprays refers the maximal number of sprays a patient has taken on a daily basis for a studied period.

The patient percentage of imputed diary days is derived for each patients as the number of non-missing diary days where morning and/or evening number of sprays are imputed to '0' to calculate the total daily dose divided by the number of non-missing diary days for a studied period and multiply by 100.

10.9 Compliance

The compliance will be derived, for each patient, during the maintenance phase, based on optimized and amended doses information as reported in the "Dose amendment" eCRF form and the total daily number of sprays derived from the eDiary as the sum of morning and evening number sprays applying missing data rule imputation on non-missing diary days as described in [Section 10.8.2](#).

A compliant day, is defined for each patient as a day when the total number of sprays taken is

- Within +/- 1 (and between 1 and 12) of the patients' optimized dose range as defined in [Table 10.9-1](#) when sprays are taken outside of an amended dose period,
- Equal to the amended dose +/- 1 (and between 1 and 12) when sprays are taken between start and stop date of an amended dose period as collected in the eCRF.

The compliance will then be defined as

$$100 * \left(\frac{\text{number of compliant days}}{\text{number of days with non-missing total daily dose information within the study period}} \right)$$

Table 10.9-1 Optimized Daily Dose and Allowed Optimized Dose Range

Optimized dose	Maximal allowed dose	Minimal Allowed dose
1	2	1
2	3	1
3	4	2
4	5	3
5	6	4
6	7	5
7	8	6
8	9	7
9	10	8
10	11	9
11	12	10
12	12	11

The rate of "0" total daily spray is defined at patient level as

$$100 * \left(\frac{\text{number of days with total daily dose= 0}}{\text{study period duration*}} \right)$$

The rate of "> 12" total daily spray is defined at patient level as

$$100 * \left(\frac{\text{number of days with total daily dose is >12}}{\text{study period duration*}} \right)$$

The rate of missing diary day IMP information is defined for each patient as:

$$100 * \left(\frac{\text{number of days with missing diary dosing information}}{\text{study period duration*}} \right)$$

Using missing morning and/or evening number of sprays information from either missing diary day and non-missing diary day (as defined in [Section 10.8.2](#))

* The study period duration refers to either the titration phase duration or the maintenance phase duration for period.

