### **9.1.2.3 Visit 4 (Day 15) and Visit 5 (Day 21)**

Visits 4 and 5 will occur 14 and 20 days after the first dose of IMP, respectively. A visit window of  $\pm$ 1 and  $\pm$ 2 days, respectively, from the scheduled visit date is permitted, but it is preferred that the visit is performed on the scheduled visit day, where possible.

Once a stable daily dose has been reached, patients should gradually decrease the interval between sprays to a target interval of approximately 1 minute between sprays. Patients should continue IMP administration at the same dose level achieved at the end of titration (i.e., their

daily optimized dose) ±1 spray divided into a morning dose and an evening dose for approximately 7 days (maintenance-dose phase). Administration of the morning and evening doses of IMP should be maintained around the same time of each day in a consistent manner in relation to food consumption, i.e., within 30 minutes after starting a snack or meal.

On Visit 5, patients will administer their morning dose of IMP with a standardized snack containing at least 300 kcal (of which approximately 30 kcal is composed of fat) at the trial site under the supervision of site staff. The IMP will not be administered in the evening of Visit 5 (Day 21).

The following assessments/procedures will be performed at these visits, unless otherwise indicated:

- MAS assessment (Visit 5 [3 hours ±15 minutes after the first spray of the morning dose] only)
- T25FW test (Visit 5 only)
- Concomitant medications review
- AE review
- Physical examination (Visit 5 only)
- Examination of the oral mucosa
- Vital signs measurement
- 12-lead ECG (Visit 5 only)
- Clinical laboratory sampling (hematology and biochemistry) (Visit 5 only)
- PK blood sampling for IMP ([Section 9.2.12.1](#))
- MSSS-88 assessment (Visit 5 only)
- C-SSRS assessment
- IMP dosing at the investigational site (Visit 5 [morning] only)
- IMP dispensing (Visit 4 only)
- IMP collection and compliance review ([Section 9.2.16](#))

The exact time of PK blood sampling and the time of the patient's snacks and meals should be recorded.

Patients should be reminded to record their 11-point NRS spasticity score, spasm count, use of antispasticity medications, and IMP dosing in the electronic diary once daily, around the same time each day, preferably in the evening before retiring to sleep.

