#### **9.1.4.3 Visit 8 (Day 45) and Visit 9 (Day 51, End of Treatment)**

Visits 8 and 9 will occur 44 and 50 days after the first dose of IMP, respectively. A visit window of  $\pm 1$  and  $\pm 2$  days, respectively, from the scheduled visit date is permitted, but it is preferred that the visit is performed on the scheduled visit day, where possible.

Once a stable daily dose has been reached, patients should gradually decrease the interval between sprays to a target interval of approximately 1 minute between sprays. Patients should continue IMP administration at the same dose level achieved at the end of titration (i.e., their daily optimized dose)  $\pm 1$  spray divided into a morning dose and an evening dose for approximately 7 days (maintenance-dose phase). Administration of the morning and evening

doses of IMP should be maintained around the same time of each day in a consistent manner in relation to food consumption, i.e., within 30 minutes after starting a snack or meal.

On Visit 9, patients will administer the morning dose of IMP with a standardized snack containing at least 300 kcal (of which approximately 30 kcal is composed of fat) at the trial site under the supervision of site staff. The IMP will not be administered in the evening of Visit 9 (Day 51).

The following assessments/procedures will be performed at these visits, unless otherwise indicated:

- MAS assessment (Visit 9 [3 hours  $\pm$ 15 minutes after the first spray of the morning dose] only)
- T25FW test (Visit 9 only)
- Concomitant medication review
- AE review
- Physical examination (Visit 9 only)
- Examination of the oral mucosa
- Vital signs measurement
- 12-lead ECG (Visit 9 only)
- Clinical laboratory sampling (hematology and biochemistry) (Visit 9 only)
- PK blood sampling for IMP ([Section 9.2.12.1](#))
- MSSS-88 assessment (Visit 9 only)
- C-SSRS assessment
- IMP dosing at the investigational site (Visit 9 [morning] only)
- IMP dispensing (Visit 8 only)
- IMP collection and compliance review

The exact time of PK blood sampling and the time of the patient's snacks and meals should be recorded.

Patients should be reminded to record their 11-point NRS spasticity score, spasm count, use of antispasticity medications, and IMP dosing in the electronic diary once daily, around the same time each day, preferably in the evening before retiring to sleep.

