^b A comprehensive physical examination, including an assessment of height, will be completed at Screening (Visit 1) only; subsequent physical examinations will be symptom-directed.

^c Serum pregnancy test at Visits 1 and 10; urine pregnancy test at Visits 2 and 6 (pre-dose).

^d On the day before PK blood sampling at Visits 4, 5, 8, and 9, patients will be prompted to record whether they started their morning and evening doses of IMP within 30 minutes of a snack or meal. On the day of PK blood sampling, the exact time and date of PK blood sampling and the time of the patient's snacks and meals should be recorded for the PK blood sampling schedule (see [Table 8.1-3](#)). Please note that more than one PK sample may be collected at distinct time points during a single visit.

^e Patients will record their 11-point NRS spasticity score, spasm count, and use of antispasticity medications in an electronic diary once daily, around the same time each day, preferably in the evening before retiring to sleep, for at least 7 days prior to Visits 2 and 6 and throughout the trial until Visit 9. Investigational medicinal product dosing will be recorded by the patient in an electronic diary from Visits 2 through 9.

^f MAS assessments will occur at Visit 1 (Screening) and at scheduled time points before (Visits 2 and 6 [pre-dose]) and after (Visits 2, 5, 6, and 9 [3 hours \pm 15 minutes post-dose]) IMP administration; for Visits in which the morning dose consists of more than 1 spray (Visits 5 and 9), post-dose assessments will occur 3 hours \pm 15 minutes after the first spray of the morning dose.

^g Non-ambulatory patients are not expected to perform the T25FW test.

^h IMP administration of the morning dose will occur at the trial site within 30 minutes after a standardized snack containing at least 300 kcal (of which approximately 30 kcal is composed of fat) under the supervision of site staff. On the days of scheduled MAS assessments other than Visit 1, patients who are taking antispasitic therapy should take their regular morning dose at least 1 hour before administration of IMP; IMP will not be administered in the evening of Days 21 and 51.

ⁱ In cases where patients are not able to attend study visits due to special circumstances (e.g., COVID-19 pandemic), the investigator will discuss with the Sponsor potential mitigation approaches for IMP dispensing, secure delivery, and collection.

Table 8.1-3 Pharmacokinetic Blood Sample Schedule

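### SAP 10.9 scores the morning-only Visit 5/Visit 9 day against the whole daily dose, so a fully adherent patient on 6 to 12 sprays with a balanced split and a filled diary scores 6/7 = 85.7%, not 100%

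*SAP*

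**What the plan says.** SAP 10.9 derives compliance in the maintenance phase. A compliant day "is defined for each patient as a day when the total number of sprays taken is" in one of two ranges. Outside an amended-dose period the test is "Within +/- 1 (and between 1 and 12) of the patients" and then refers to the optimized dose range in Table 10.9-1. The other branch applies "when sprays are taken between start and stop date of an amended dose period as collected in the eCRF". The day's total is morning plus evening sprays, and the denominator is the "number of days with non-missing total daily dose information within the study period".

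SAP 10.8.1 starts the phase at Visit 4 (Visit 8 in Period 2). It ends it in Period 1 at "Min(Visit 5 date, the date of the last dose of study drug" and in Period 2 at the last-dose date. SAP 10.8.2 counts both end dates, and turns a blank morning or evening entry on a filled diary day into 0.

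For the visit day itself, SAP Table 8.1-2, footnote h, says "IMP will not be administered in the evening of Days 21 and 51". Protocol 9.1.2.3 says "The IMP will not be administered in the evening of Visit 5 (Day 21", and Protocol 9.1.4.3 says "The IMP will not be administered in the evening of Visit 9 (Day 51". Protocol 8.1.2 asks patients on a stable dose to aim for an even morning/evening split.

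SAP 12.3.1.3 reports compliance by treatment arm in four bands: below 80%, 80% to below 90%, 90% to below 100%, and exactly 100%.

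**The concern.** The last day of the phase is planned as roughly half a day's dosing but is judged as a full day. SAP 10.9 has no exception for it. SAP Appendix 1 does treat the day as special: major deviation 10 asks only for at least one morning spray on it. The compliance definition has no matching rule.

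At stake is the meaning of the compliance table. A patient who does what the protocol asks is recorded as non-compliant on one day in each period, and the top band cannot be reached over most of the dose range. One real lapse can also move a patient into a lower band than the lapse alone would justify.

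**Working it through.** **Inputs.** Table 10.9-1 is reproduced in all 12 rows by minimum = max(1, D − 1) and maximum = min(12, D + 1), where D is the optimized dose (D = 4 gives 3 to 5; D = 12 gives 11 to 12). Phase length is stop − start + 1 (SAP 10.8.2): 21 − 15 + 1 = 7 days in Period 1 and 51 − 45 + 1 = 7 in Period 2. Visit-day sprays under an even split are D/2, rounded either way if D is odd, and at least 1.

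**Two readings of the tolerance.** SAP 10.9 applies plus or minus 1 to a table range that already contains plus or minus 1. Reading A uses the table as printed. Reading B adds a second plus or minus 1, so the minimum becomes max(1, D − 2).

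| D | Visit-day sprays | Minimum, A | Day under A | Minimum, B | Day under B |
|---|---|---|---|---|---|
| 1 | 1 | 1 | passes | 1 | passes |
| 2 | 1 | 1 | passes | 1 | passes |
| 3 | 1 or 2 | 2 | passes only with 2 | 1 | passes |
| 4 | 2 | 3 | fails | 2 | passes |
| 5 | 2 or 3 | 4 | fails | 3 | passes only with 3 |
| 6 | 3 | 5 | fails | 4 | fails |
| 7 | 3 or 4 | 6 | fails | 5 | fails |
| 8 | 4 | 7 | fails | 6 | fails |
| 9 | 4 or 5 | 8 | fails | 7 | fails |
| 10 | 5 | 9 | fails | 8 | fails |
| 11 | 5 or 6 | 10 | fails | 9 | fails |
| 12 | 6 | 11 | fails | 10 | fails |

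Every even split fails at 9 of 12 dose levels under A (4 to 12) and at 7 of 12 under B (6 to 12). Doses 6 to 12 fail on both.

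**Score of a fully adherent patient, nominal phase.** 6 compliant days / 7 days = 85.7%, in the 80% to below 90% band. Without the visit day: 6/6 = 100%.

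**Permitted visit dates.** Visit 4 may fall on Days 14 to 16 and Visit 5 on Days 19 to 23, with the same offsets in Period 2. The phase then lasts from 19 − 16 + 1 = 4 to 23 − 14 + 1 = 10 days. The score (n − 1)/n for n = 4, 5, 6, 7, 8, 9, 10 is 75.0, 80.0, 83.3, 85.7, 87.5, 88.9 and 90.0%. It never reaches 100%.

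**One truly missed, recorded day, nominal phase.** 5/7 = 71.4% (below 80%) as written, against 5/6 = 83.3% (80% to below 90%) without the visit day.

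**The case against.** Several escape routes exist, and each narrows the claim.

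- If the visit-day diary is blank, the day leaves the denominator and the score is 6/6. The protocol asks for dosing entries until Visit 9, so this is not the planned case.
- The amended-dose branch would pass the day if the site logged it as an amendment. Neither document tells sites to log the planned evening omission, but form-completion instructions are not available here.
- The even split is an aim, not a requirement. A day with at most one evening spray planned, such as 4 taken as 3 + 1, passes.
- The day passes in some cases if one extra spray is planned within the allowed variation: 4 taken as 3 + 2 under reading A, 6 taken as 4 + 3 under reading B.
- If the last dose fell on an earlier full-dose day, the phase ends there and nothing is lost.

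The remaining objections concern harm, and they largely stand. A reader might infer that the output cannot tell the adherent patient from one on 1 or 2 sprays who really missed a day, since both score 6/7. The documents do not support this. A recorded missed day at those doses has 0 sprays, so the zero-spray rate reported alongside is 1/7 = 14.3% for that patient and 0/7 for the adherent one. The planned plot of mean sprays by day (SAP 12.3.1.2) would also show the final-day drop.

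A reader might also infer a bias between arms. Each completer has the same morning-only last day under both treatments. A difference would need the dose mix, diary completion or phase length to differ by arm, and the documents give no figures for these.

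**Conclusion.** The defect is real and of low severity. It requires a filled visit-day diary, an even split taken as planned, and no amended dose logged for that day. Doses 6 to 12 are affected on either reading. Extending this to 4 and 5 for every even split depends on reading A, which the printed limits of Table 10.9-1 and the protocol's one-spray allowance favour but the sentence in SAP 10.9 does not settle.

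The effect depends on dose and is present in both arms. How many patients it touches cannot be derived from the documents.

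A reader might infer that the efficacy analyses are contaminated. They are not. Percentage compliance is not among the major deviations in SAP Appendix 1, so the Per Protocol set is unaffected, and it does not enter the Full Analysis Set or the primary model. Whether it will be reported at all is open: the SAP addendum's table for abbreviated reporting neither lists compliance nor says that it is dropped.

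**What to change.** Add one sentence to SAP 10.9: the Visit 5 or Visit 9 day on which only the morning dose is planned is excluded from both numerator and denominator of the compliance ratio. The fully adherent patient then scores 6/6 = 100%, and one missed day gives 5/6 = 83.3%.

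Leave the phase dates in SAP 10.8.1 unchanged, so that major deviation 10 and the note to Table 10.1-3 placing the Day 21 assessment in the maintenance phase stay intact.

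Scoring the day against the planned morning dose would also give 100% (7/7) and keep the supervised dose in the ratio. However, the SAP describes the optimized dose as a daily number without a planned morning share, so that route needs a further rule.

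The cost is one sentence and no new data. The denominator loses at most one day per period, and none where the visit-day diary is blank or the last dose came earlier. If compliance is not reported after early termination, nothing need be done.
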